### **13.3.4. Secondary Efficacy Endpoints**

Time to event secondary endpoints will be analyzed by stratified log-rank test. Binary endpoints will be compared between treatments via the same logistic regression model as for the primary efficacy endpoints. Continuous secondary endpoints will be compared via analysis of covariance for a model including factors for treatment, strata, and baseline covariate if available, or non-parametric rank tests if normality or homogeneity assumptions appear substantially violated. Overall study-wise type 1 error control across secondary endpoints will be addressed via step-down testing. That is, the secondary endpoints will be tested one at a time in step-down order, until the first non-significant result, after which step-down testing will stop for purposes of supporting conclusions.

Individual patient listings will be provided for the primary and secondary endpoints.

### **13.3.5. Safety Analysis**

#### **13.3.5.1. Adverse Events**

All treatment emergent adverse events (TEAEs) recorded during the study will be coded according to Medical Dictionary for Regulatory Activities and all AEs will be listed. Treatment emergent is defined as any adverse event that emerges after the subject is enrolled in the study. TEAEs will be tabulated by system organ class (SOC), and individual preferred terms within each SOC. The crude incidence rate of patients who experienced AEs coded with the same preferred term will be tabulated by treatment group. TEAEs will also be tabulated by worst experienced severity. A separate summary will present treatment-emergent AEs judged related (missing relationship is considered as related) to study treatment.

Adverse events leading to premature discontinuation from the study will be listed and summarized in a manner similar to that used for TEAEs.

SAEs will be listed and summarized in a manner similar to that used for TEAEs, separated into treatment-emergent SAEs, and SAEs occurring before successful creation of the AV fistula and after.

Reasons for death will be listed and summarized in a manner similar to that used for AEs, separated for treatment-emergent deaths.

Reasons for premature discontinuation from the study will be listed and summarized by frequency tables.

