g Access assessment to document fistula patency and fistula development status. Evaluations include thrill and bruit assessment, arm elevation test, and augmentation test. Access assessments should be performed by delegated dialysis unit personnel.

h Clinical exam to document wound healing, any local problems such as infection, wound dehiscence, unexpected amount of arm swelling, etc., and evaluation for presence of steal syndrome (e.g. pain in digits, discoloration, cold fingers, blue fingers, etc.).

i For subjects on hemodialysis at the time of enrollment or subjects who initiate dialysis within 28 days of index procedure, cannulation assessment will start no earlier than 28 days post index procedure with subsequent assessments occurring at discretion of the investigator and/or designee. The decision to proceed with first cannulation will be based on the investigator's clinical assessment.

j For subjects who do not initiate hemodialysis by Day 90 and the index fistula has not been abandoned, a duplex ultrasound must be performed at the 3 month follow up visit.

k For subjects whose index fistula is not in use for hemodialysis on day 150 and the index fistula has not been abandoned, a duplex ultrasound must be performed at the 6 month follow up visit.

l For subjects whose index fistula is not in use for hemodialysis on day 330 and the index fistula has not been abandoned, a duplex ultrasound must be performed at the 12 month follow up visit.

m Record adverse events and concomitant medications that are associated with or occurred during an SAE or vascular access events. See sections 9.7 and 12.

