## **11. ASSESSMENT OF SAFETY**

Safety evaluations will be based on treatment emergent adverse events (TEAEs) up to the 2 month visit and vascular access events reported during the study. Treatment emergent is defined as any adverse event that emerges after the subject is enrolled (run-in and randomized) in the study. The run-in subjects' adverse events will be included in the safety evaluation. Vascular access events include access dysfunction, thrombosis, access-related hand ischemia, infiltration requiring a rest period, fistula-related bleeding, infection, problems with wound healing, aneurysm, pseudoaneurysm, and all interventional procedures performed on the study fistula. During follow-up, after the 2 month visit, the following will be reported and recorded: vascular access events, concomitant medications and therapies associated with vascular access, serious adverse events (SAEs) and AEs reported during an SAE. At each follow-up visit up to the 2 month visit, AEs and concomitant medications will be recorded. Changes in comparison to baseline and the 2 month visit that are considered to be clinically significant will be reported as AEs.

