### **12.2. Collection and Recording of Adverse Events**

#### **12.2.1. Collection of Adverse Events**

The investigator must monitor the condition of the subject throughout the study from the time of obtaining informed consent until the last visit. Findings from assessments and examinations done during screening are not AEs, but are recorded as medical history. Safety evaluations will be based on treatment emergent adverse events (TEAEs) up to the 2 month visit and vascular access events reported during the study. Vascular access events include access dysfunction, thrombosis, access-related hand ischemia, infiltration requiring a rest period, fistula-related bleeding, infection, problems with wound healing, aneurysm, pseudoaneurysm, and all interventional procedures performed on the study fistula. Treatment emergent is defined as any adverse event that emerges after the subject is enrolled (run-in and randomized) in the study. Following the 2 month visit the following will be reported and recorded: vascular access events, concomitant medications and therapies associated with vascular access, serious adverse events (SAEs) and AEs reported during an SAE.

The sources of AEs may cover:

- The subject's response to questions about his/her health (a standard non-leading question such as "How have you been feeling since your last visit?" is asked at each visit)

- Symptoms spontaneously reported by the subject
- Investigations and examinations where the findings are assessed by the investigator to be clinically significant changes or abnormalities
- Other information relating to the subject's health becoming known to the investigator (e.g., hospitalization, etc.)

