### **12.2.2. Recording of Adverse Events**

The investigator must record all AEs in the Adverse Event Log provided in each subject's eCRF from the time of enrollment up to the 2 month visit. Following the 2 month visit through end of study, reporting requirements change to only reportable AEs (vascular access events and SAEs). Information to be recorded includes:

- Adverse event
- Date of onset
- Severity
- Causal relationship to investigational product
- Action taken to investigational product
- Other action taken
- Date of outcome
- Outcome
- Seriousness

Each of the items in the Adverse Event Log is described in detail in the following sections.

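### Section 13.3.5.1 sets no time window for the general TEAE tables, although the protocol elsewhere stops that evaluation at the 2 month visit and recording of other non-serious AEs becomes conditional after it

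*Combined protocol and SAP*

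**What the plan says.** **Analysis.** Section 13.3.5.1 opens with "All treatment emergent adverse events (TEAEs) recorded during the study will be coded" and says that all AEs will be listed. It then states: "Treatment emergent is defined as any adverse event that emerges after the subject is enrolled in the study". For the tables it says: "The crude incidence rate of patients who experienced AEs coded with the same preferred term will be tabulated by treatment group". Worst severity and relatedness are also tabulated. None of these sentences carries an end date. SAEs get their own summary.

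**Evaluation window.** Section 11 says: "Safety evaluations will be based on treatment emergent adverse events (TEAEs) up to the 2 month visit and vascular access events reported during the study". The Synopsis and Section 12.2.1 give the same 2 month limit.

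**Recording after the 2 month visit.** Three rules appear:
- Table 7, footnote m: "Record adverse events and concomitant medications that are associated with or occurred during an SAE or vascular access events".
- Synopsis, Section 11 and Section 12.2.1: vascular access events, SAEs, and other AEs only if they are reported during an SAE.
- Section 12.2.2: "reporting requirements change to only reportable AEs (vascular access events and SAEs". Section 9.7 describes reportable AEs in the same way.

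**The concern.** A programmer who follows Section 13.3.5.1 as written has no reason to stop the tables at month 2. For a preferred term that is not an access event, the count would then combine two months of complete recording with about ten months in which a non-serious event is recorded only under some condition, or not at all. The result estimates no defined risk period.

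A second problem arises if the condition is itself affected by treatment. Section 5.4 expects the implant to reduce the need for supplementary interventions, and Section 11 counts every interventional procedure on the study fistula as an access event. Under footnote m, an access event is an occasion for other AEs to be recorded. If the arms differ in access events, they differ in those occasions, even though the written rule is the same for both. At stake is whether the between-arm AE table in the study report can be interpreted.

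**Working it through.** The plan states no AE or access-event rate, so there is no figure of its own to reproduce. The main check is a comparison of the text.

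**Step 1: the window.** Section 13.3.5.1 gives none. The Synopsis and Sections 11 and 12.2.1 give the 2 month visit. Section 13.3.5.1 neither repeats that limit nor refers to it.

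**Step 2: what a whole-study row would contain for a non-access preferred term.**

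| Rule after month 2 | Other non-serious AEs | Content of the row | Can recording differ by arm through access events? |
|---|---|---|---|
| Table 7, footnote m | With an SAE or access event | Complete to month 2, then conditional | Yes, if access events differ |
| Synopsis, Sections 11 and 12.2.1 | During an SAE only | Complete to month 2, then conditional | Possibly: Section 12.3.1 makes hospitalization an SAE, and Section 5.1 calls access complications the leading cause of hospitalization |
| Section 12.2.2 | Not recorded | Non-serious cases from 2 months plus serious cases from 12 | Not by this route |

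Under all three rules the row is neither a 2-month nor a 12-month risk. Access events and SAEs are recorded throughout in both arms, so their own whole-study rates are unaffected.

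**Step 3: when the arms can diverge.** Let A be the risk of the AE to month 2, B the risk from month 2 to 12, c the probability of a recording trigger after month 2, and s the share of later AEs captured when a trigger occurs. If trigger and AE are independent, recorded incidence is

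R = 1 − (1 − A)(1 − B × c × s).

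With A, B and s equal in both arms, R differs only if c differs. If s = 0 (no other AEs recorded) or the table stops at month 2, R = A in both arms.

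**Step 4: illustration of the mechanism; every input is assumed.** Take a true incidence of 20% per year in both arms and a constant hazard over 360 days.
- A = 1 − 0.80^(60/360) = 3.7%; B = 1 − 0.80^(300/360) = 17.0%.
- Take c = 0.55 for control and 0.35 for implant. These are one minus the planning FSD6 rates of 45% and 65%, used only as a stand-in.
- s = 1: control 12.6%, implant 9.4%.
- s = 0.5: control 8.1%, implant 6.5%.
- c = 0.50 in both arms: 11.8% in each at s = 1, 7.7% in each at s = 0.5.
- Table stopped at day 60: 3.7% in each.
- Values of c exchanged, s = 1: control 9.4%, implant 12.6%. The direction reverses.

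With yearly incidence of 10%, 20% or 40%, triggers of 55% vs 24%, 55% vs 35% or 70% vs 50%, and s of 0.5 or 1, the implant/control ratio runs from 0.59 to 0.84 with no true difference. These values of s are generous: the model captures half or all of a triggered subject's AEs over 300 days, whereas footnote m covers only those tied to the event. The exercise shows that a distortion is possible. It does not estimate one.

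**The case against.** The best reply is that the documents can be read together. The words about everything recorded during the study govern coding and listing, not the incidence tables. The table sentences are silent on the window, and the protocol states the 2 month limit three times elsewhere. On that reading everything is coded and listed, and general TEAEs are evaluated only to month 2. This stands as far as it goes: a reader might infer that the plan sets out to pool 12 months of TEAEs, and the text does not establish that. What remains is that the analysis section defines treatment emergence without an end date and leaves the reader to import the limit.

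Second, the link from access events to other AEs rests on footnote m alone. That footnote refers to Sections 9.7 and 12, whose rules are narrower. This also stands, and it limits the differential-recording concern to footnote m and, less directly, to the SAE trigger. It does not remove the mixed risk period, and it shows that the recording rules themselves disagree.

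Third, Section 13.1 leaves full details to a SAP. The document reviewed contains no separate SAP text, so a cut-off there cannot be ruled out. Section 13.1 also makes Section 13 the basis of that SAP, so the gap could carry forward.

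Finally, the AE tables are descriptive, no test is planned on them, and SAEs are already summarised separately. That lowers the stakes.

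**Conclusion.** Section 13.3.5.1 conflicts with the Synopsis and Sections 11 and 12.2.1 on the window for general TEAE tables, and the rule for recording other non-serious AEs after month 2 has three versions. Taken literally, the analysis section would produce rates that correspond to no defined risk period. Under footnote m, and possibly under the SAE trigger, ascertainment of non-access, non-serious AEs could also differ by arm. That requires two things: the tables are run past month 2, and the implant changes access events.

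A reader might infer that the implant will look safer than it is by some number of points. For example, assume access events after month 2 in 50% of controls and 30% of implant subjects, with 10% to 30% of those events bringing in another AE: (0.50 − 0.30) × 0.10 to 0.30 gives 2 to 6 points. The documents do not support such a figure. None of the inputs is in them. The sum matches no row the plan specifies: the extra AEs would be spread over many preferred terms, and a subject with an access event already counts in any overall TEAE row. The direction also depends on which arm has more access events. Neither size nor direction can be derived.

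The point should be corrected before the tables are programmed, because it resolves an internal contradiction at almost no cost.

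**What to change.** In Section 13.3.5.1 (and in the SAP, if it is separate):
1. Restrict the general TEAE tables (SOC and preferred term, worst severity, relatedness) to onset up to the 2 month visit. State a study-day cut-off for subjects who miss it, for example day 64, the upper end of the 60 ± 4 day visit window (60 + 4).
2. Tabulate SAEs and vascular access events separately over the whole study, each with severity and relatedness, so that late related events stay in the summaries.
3. List other non-serious AEs recorded after the 2 month visit, but keep them out of between-arm incidence.
4. Reconcile the rules for recording after month 2 in Table 7 footnote m, in the Synopsis with Sections 11 and 12.2.1, and in Section 12.2.2, so that one rule applies throughout.

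The cost is a wording change and a date cut-off in the table programs. The small downside is that late non-access, non-serious AEs appear only in listings.

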#### **13.3.5.2. Baseline Variables and Concomitant Medications**

Continuous demographic variables (e.g., age, weight) and disease characteristics (e.g., time since diagnosis, etc.) will be summarized using descriptive statistics. Qualitative demographic characteristics (e.g., sex, race) and disease characteristics will be summarized by counts and percentages. Other baseline patient characteristics (e.g., medical history) will only be listed. All medications will be coded according to the WHO drug code and the drug-class code. They will

be summarized for each treatment group, the number and percentages of subjects having received each medication.

### **13.3.6. Exploratory Analyses**

Exploratory data-driven analyses can be performed with the caveat that any statistical inference will be of supportive nature rather than confirmatory.

## **14. DIRECT ACCESS TO SOURCE DATA/DOCUMENTS**

### **14.1. Study Monitoring**

Before an investigational site can enter a patient into the study, a representative of the sponsor and/or designee will evaluate the investigational study site to:

- Determine the adequacy of the facilities
- Discuss with the investigator(s) and other personnel their responsibilities with regard to protocol adherence, and the responsibilities of the sponsor and/or designee. This will be documented in a Clinical Study Agreement between the sponsor and the investigator.

During the study, a monitor from the sponsor and/or designee will have regular contact with the investigational site, for the following:

- Provide information and support to the investigator(s)
- Confirm that facilities remain acceptable
- Confirm that the investigational team is adhering to the protocol, ICH-GCP, applicable SOPs, and regulatory requirements that data are being accurately recorded in the eCRF, and that investigational product accountability checks are being performed
- The Investigator will permit the monitor timely access to all data needed to perform source data verification. This includes a comparison of the data in the eCRF with the patient's medical records at the hospital or practice, and other records relevant to the study. This will require direct access to all original records for each patient (e.g., clinic charts) and dialysis runsheets.
- Record and report all protocol deviations
- Confirm AEs and SAEs have been properly documented on eCRFs and confirm any SAEs have been forwarded to the sponsor and/or designee and those SAEs that met criteria for reporting have been forwarded to the IRB

The Investigator is expected to be able to meet with the monitor during these visits. The monitor will be available between visits if the investigator(s) or other staff needs information or advice.

## **14.2. Audits and Inspections**

Authorized representatives of the sponsor, a regulatory authority, or an Institutional Review Board may visit the site to perform audits or inspections, including source data verification. The purpose of a sponsor audit or inspection is to systematically and independently examine all study-related activities and documents to determine whether these activities were conducted, and data were recorded, analyzed, and accurately reported according to the protocol, Good Clinical Practice guidelines of the International Conference on Harmonization, and any applicable regulatory requirements. The investigator should contact the sponsor and/or designee immediately if contacted by a regulatory agency about an inspection.

## **14.3. Confidentiality of Subject Data**

Information about study subjects will be kept confidential and managed according to the requirements of the Health Insurance Portability and Accountability Act of 1996 (HIPAA). In the event that a subject revokes authorization to collect or use protected health information (PHI), the investigator, by regulation, retains the ability to use all information collected prior to the revocation of subject authorization. For subjects that have revoked authorization to collect or use PHI, attempts should be made to obtain permission to collect at least vital status (i.e. that the subject is alive) at the end of their scheduled study period.

# **15. QUALITY CONTROL AND QUALITY ASSURANCE**

To ensure compliance with Good Clinical Practices and all applicable regulatory requirements, the sponsor and/or designee may conduct a quality assurance audit. Please see Section [14.2](#) for more details regarding the audit process.

## **15.1. Protocol Amendments**

Any change to this Protocol will be documented in a Protocol Amendment, issued by the sponsor, and approved by the IRB prior to its implementation.

Substantial amendments will be submitted for consideration to the approving IRBs and Regulatory Authorities, in accordance with local regulations. An approval is required for a Substantial Amendment, e.g., one which could affect the safety of the subjects, or which entails a change to the scope/design of the study, or where a new principal or coordinating investigator is included.

## **15.2. Deviations from the Protocol**

Deviations from the protocol should not occur. If deviations occur, the investigator must inform the monitor, and the implications of the deviation must be reviewed and discussed. All deviations

must be documented (or included in eCRF data). There should be a description of the deviation, the relevant time points (visit numbers, start and stop), reason for deviation, and the corrective action taken. Deviation reports and supporting documentation must show documentation of PI review and be kept in the Investigator's File and in the Trial Master File and recorded into the eCRF.

### **15.3. Premature Study Termination**

Both the investigator (with regard to his/her participation) and the sponsor reserve the right to terminate the study at any time. Should this become necessary, the procedures will be agreed upon after consultation between the two parties. In terminating the study, the sponsor and the investigator will ensure that adequate consideration is given to the protection of the best interests of the subjects. Regulatory authorities and IRB's will be informed.

In addition, the sponsor reserves the right to terminate the participation of individual study sites. Conditions that may warrant termination include, but are not limited to, insufficient adherence to protocol requirements and failure to enter subjects at an acceptable rate.

## **16. ETHICS**

### **16.1. Ethical Conduct of the Study**

This study will be conducted in accordance with Good Clinical Practice (GCP) requirements described in the current revision of International Conference on Harmonisation of Technical Requirements of Pharmaceuticals for Human Use (ICH) Guidelines and all applicable regulations, including current United States Code of Federal Regulations (CFR), Title 21, Parts 11, 50, 54, 56, and 312 and Title 45, Part 164. Compliance with these regulations and guidelines also constitutes compliance with the ethical principles described in the current revision of the Declaration of Helsinki. This study will also be carried out in accordance with local legal requirements.

### **16.2. Ethics Review**

The final study protocol, including the final version of the Informed Consent Form, must be approved or given a favorable opinion in writing by an IRB as appropriate. The investigator must submit written approval to the sponsor and/or designee before he or she can enroll any subject into the study.

The investigator and/or designee is responsible for informing the IRB of any amendment to the protocol in accordance with local requirements. In addition, the IRB must approve all advertising used to recruit subjects for the study. The protocol must be re-approved by the IRB upon receipt of amendments and annually, as local regulations require.

The investigator and/or designee is also responsible for providing the IRB with reports of any reportable serious adverse drug reactions from any other study conducted with the investigational product. The sponsor and/or designee will provide this information to the investigator.

Progress reports and notifications of serious adverse drug reactions will be provided to the IRB according to local regulations and guidelines.

